Transthoracic needle aspiration (TTNA) is currently the preferred mode for sampling peripheral pulmonary nodule (PPN) because it has a high diagnostic yield ranging from 80% to 90% [2]. However, it has a 12% to 45% risk of pneumothorax, with 2% to 15% requiring chest tube placement [3]. Flexible bronchoscopy with brushing, washing, and transbronchial biopsy (TBB) is safe but provides a much lower diagnostic yield (14 to 63%) depending on the size and location of PPN [4,5]. A recent meta-analysis including 1033 PPNs revealed that the diagnostic yield of TBB can reach up to 65%, if guidance systems such as electromagnetic navigational bronchoscopy (ENB), virtual bronchoscopy (VB), or radial-probe ultrasound (r-EBUS) are used. However, the negative predictive value (NPV) was reported to be low (0.52) [6,7].

Robotic technology has recently been incorporated into navigational bronchoscopy to improve flexibility, reach, and stability [8,9]. While manual and robot-assisted navigational bronchoscopy technologies have been proven effective in directing the bronchoscopist to achieve proximity to peripheral nodules, further localization with radial ultrasound and/or fluoroscopy is often required to make fine adjustments to align the biopsy needle with the target nodule. Without independent confirmation that a needle is in the lesion, a bronchoscopic lung biopsy that does not show tumor cells is often considered non-diagnostic rather than negative. Needle biopsies may therefore require multiple needle passes, which can cause bleeding. While rarely life-threatening, bleeding can contaminate slides and make a rapid on-site evaluation (ROSE) of biopsy samples challenging. A technology offering independent confirmation that the tip of the needle is within the nodule may reduce the incidence of non-diagnostic biopsies.

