- b. The number and frequency of nCLE procedure-related AE/SAE from the start of the procedure until end of 12-month follow-up
- 8. To assess the reproducibility of nCLE criteria to the reference standard. Three nCLE characteristics for the detection of malignancy were identified during Wijmans et al. study [10]:
 - a. Dark enlarged pleomorphic cells;
 - b. Dark cell clusters consist of overlapping cell structures ('dark clumps') and
 - c. Continuous movement of the cells in one direction ('directional streaming').
- 9. To create an nCLE image atlas for malignant characteristics in PPNs.

3. Study Design

This is a randomized, controlled, interventional, comparative prospective multi-center study. In total, a maximum of 118 consecutive patients with a (suspected) PPN who are referred for a diagnostic bronchoscopic (Robotic-guided TBNA) procedure will be considered for enrollment. The estimated duration of the study is 24 months. Patients will be consecutively recruited and randomly assigned to undergo Robotic-guided TBNA (n=59) or Robotic-nCLE-guided TBNA (n=59).

Only patients in the nCLE arm will receive intravenously administered fluorescein before the start of the Robotic procedure. During the nCLE procedure, an 18G needle enters the targeted tissue, followed by an nCLE AQ-Flex™ 19N Confocal Miniprobe™ (Mauna Kea Technologies, France) through the biopsy needle, to obtain real-time imaging. nCLE imaging will be performed in the PPNs with a total estimated time for research measurements of 10 minutes. nCLE imaging will be performed for each sequential TBNA pass/sampling within the lung nodule lesion and each TBNA path cytopathological result will be correlated with the nCLE sequence acquired for that TBNA pass. TBNA sampling will end when sufficient diagnostic material will be found with ROSE (as assessed by the cytopathologist) or when the physician performing the procedure judges that the number of samplings/passes is adequate. ROSE will be performed by a cytopathologist.

4. Study Population

Population (base)

Patients with a PPN referred for diagnostic bronchoscopic/endosonographic workup tissue sampling based on standard (PET-) CT imaging

Inclusion criteria

To be eligible to participate in this study, a study subject must meet all of the following criteria:

- ≥ 21 years of age
- Suspected PPN
- Nodule size in CT between 8 mm and 30 mm (largest dimension)

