2. First-two-passes cumulative diagnostic yield is calculated as the proportion of patients for which first-two-passes cumulative TBNA pass during the bronchoscopic procedure yielded a definitive diagnosis out of the total number of patients that have received a diagnostic procedure.
3. First-three-passes cumulative diagnostic yield is calculated as the proportion of patients for which first-three-passes cumulative TBNA pass during the bronchoscopic procedure yielded a definitive diagnosis out of the total number of patients that have received a diagnostic procedure.
4. Etc.... until the fifth pass.

The number of patients has been calculated to demonstrate an increase of the TBNA first-pass diagnostic yield by 20%, from 70% to 90%, between the Robotic-guided TBNA and the Robotic-nCLE-guided TBNA, with a statistical power of 80% with a 2-sided significance level of 0.05. A group size of 59 patients per arm has been derived. By including 59 patients in each arm, we expect to image at least 29 malignant nodules (prevalence of 0.5) in each arm.

The study will enroll 118 consecutive patients randomly assigned 1:1 to Robotic-guided TBNA arm or Robotic-nCLE-guided TBNA arm.

5. Treatment of Subjects

Investigational product/treatment

In recent years, confocal laser endomicroscopy (CLE) has emerged as a novel technique that enables *in vivo* microscopic analysis during ongoing endoscopy [24]. CLE is based on tissue illumination with a low-power laser with subsequent detection of the fluorescence light reflected from the tissue. It is a contrast-based technique, the most widely used agent being the intravenously administered fluorescein. The probe of the endomicroscopy system consists of a flexible catheter probe representing a bundle of optical fibers linked to a micro-objective, a laser scanning unit, and the control and acquisition software (Cellvizio® I.V.E system, Mauna Kea Technologies, France). The principle of the technique is based on a laser beam of the defined wavelength being focused towards the targeted tissue, and the recaptured signal is displayed as 'optical biopsies' in a single horizontal plane.

[figure not shown]

Figure 1: A- Locking of the CLE probe to the aspiration needle. B- CLE probe inside endosonography needle. C- Endosonography images of n-CLE measurements (white arrow) inside a lymph node (LN) (Wijmans/Annema et al. [10]).

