Most recently, in January 2018, Cellvizio® was recommended by the Korean National Health Agency (NECA, New Health Technology Assessment Committee) and obtained the Innovative Technology status. This recommendation was based on a systematic review of the literature on CLE and allowed the NECA to recognize endomicroscopy as "a safe and effective method that can help identify cancerous lesions and target biopsies for patients with suspected dysplasia in the esophagus, stomach, and bile duct stenosis." In this evaluation ([nHTA Report](https://nhta.neca.re.kr/nhta/publication/u0601vfd.ecg?pub_seq=572&file_kind=E) / Submission No. HTA-2018-16 *Abstract (English)* : https://nhta.neca.re.kr/nhta/publication/u0601vfd.ecg?pub_seq=572&file_kind=E, *Full text* : https://nhta.neca.re.kr/nhta/publication/u0601vfd.ecg?pub_seq=572&file_kind=F), the NECA evaluated the safety of CLE by examining 17 articles to identify complications and side effects associated with endomicroscopy with fluorescein injection. From this review, the NECA subcommittee evaluating the safety of endomicroscopy noted:

- that the complications or side effects identified in this literature review showed no difference between an endoscopy procedure without endomicroscopy and an endoscopy with endomicroscopy and fluorescein injection, and,
- most studies have not reported any serious side effects or complications.

The NECA subcommittee, therefore, concluded that the safety of the technology is of an acceptable level. So far, all the studies that investigated nCLE use showed that no adverse events occurred. Most studies investigated nCLE combined with EUS, and only one case report examined the Robotic guided nCLE and reported no adverse events.

[figure not shown]
[figure not shown]
Study procedures

Preparation before the procedure

Before beginning the procedure, a locking device is attached to the proximal end of a standard TBNA puncture needle (Bronchus 18G needle). To do so, the metallic stylet originally in the needle must be removed.

1. Removal of the stylet from the needle	2. Locking of the locking device onto the proximal needle hub
 	 

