nCLE requires the administration of exogenous fluorescent contrast. Minutes before CLE positioning, the patient will be administered 2.5 mL of 10% fluorescein IV. A repeat dosage of 2.5 ml of 10% fluorescein can be provided after 15-30 minutes to a maximum dosage of 5 ml of 10% fluorescein in total. Patients will be monitored for allergic reactions, including anaphylaxis. Fluorescein Sodium can be used as a contrast agent with Cellvizio® I.V.E system with Confocal Miniprobes™ without change of formulation, mode of action, approved dose, or route of administration. Refer to the indications for using the fluorescein to perform the injection or to chapter 1: "Fluorescein Angiography: Basic Principles and Interpretation" of Ryan et al. book on Optical Imaging Technologies [25].

The target area will then be identified on the ultrasound and/or fluoroscopy monitor and accessed in the usual manner per standard of care. Once the nodule is localized, an 18G needle with the Confocal Miniprobe™ inside will be introduced through the bronchoscope's working channel and advanced into a lung nodule. After the puncture, the AQ-Flex™ 19 N Confocal Miniprobe™ will then be advanced through the needle into the nodule. Imaging will take place, which will be evaluated by the physician performing the procedure. The on-site image interpretation will be recorded. The AQ-Flex™ 19 N Confocal Miniprobe™ will be removed, and tissue will be aspirated at the imaging site from the tip of the needle that is still in place. ROSE will be performed by the cytology team per standard of care. If no lesional tissue is identified, then the robot may be repositioned for additional needle passes. For each needle pass, a separate CLE movie will be recorded. Multiple needle passes and nCLE imaging may occur, specifically if no tumor is identified on ROSE. In the case of re-localization of the needle, nCLE imaging may be repeated before further needle aspirations. Duration will be recorded after each pass. Chest ultrasound or fluoroscopy will be performed to evaluate for pneumothorax.

7. Puncture the identified target lesion with the needle per standard of care and usual procedure (the Confocal Miniprobe™ is pre-loaded but retracted)	8. Maintain the needle as straight as possible and parallel to the working channel of the scope. (to limit the retraction of the probe within the working channel) Twist the locking device and the probe back onto the needle
	

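### The operator very probably knows the arm during navigation and localisation, steps common to both arms, so unequal effort or arm-aware exclusion could bias first-pass yield in either direction

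*Combined protocol and SAP*

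**What the plan says.** **When the arm becomes visible.** Section 3 (Study Design) says "Only patients in the nCLE arm will receive intravenously administered fluorescein before the start of the Robotic procedure". The numbered list of standard and study procedures in Section 5 puts the dye at step 2, ahead of bronchoscope introduction (step 4) and target localisation (step 5). The narrative under Steps during the procedure ties the dye to the minutes before probe positioning, but still describes it ahead of target identification. For the device, Preparation before the procedure says "Before beginning the procedure, a locking device is attached to the proximal end of a standard TBNA puncture needle", followed by probe loading.

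**What the arms share.** In the numbered list only steps 2 (dye) and 6 (imaging) are marked as research. Navigation, localisation and, in step 5, needle introduction under fluoroscopy and r-EBUS are standard in both arms. The Summary (Rationale) notes that "further localization with radial ultrasound and/or fluoroscopy is often required to make fine adjustments to align the biopsy needle with the target nodule".

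**Masking.** Section 8 keeps the pathologists unaware of nCLE results, and Section 5 blinds the video raters. No masking of the operator is described, and no time is given for randomisation or disclosure.

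**Endpoint and exclusions.** The primary endpoint is first-pass yield among patients who received a diagnostic procedure. Under the intra-operative criteria in Section 4, a lesion that cannot be localised or confirmed is an exclusion. Navigation success is the investigator's own assessment (Section 7).

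**The concern.** The primary endpoint rests on one needle pass. How well the robot is positioned before that pass depends on the operator and precedes any contribution from imaging. If the operator knows the arm, effort on this shared step may differ between arms, and the difference would be counted as an nCLE effect or would hide one.

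There is a second route. Deciding that a lesion cannot be localised removes the patient from the procedure and, as the denominator is worded, perhaps from the analysis. Made with knowledge of the arm, that decision can alter who is counted.

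Masked pathologists guard against biased reading of the sample. They do not guard against unequal placement of the needle or unequal exclusion. The planned comparisons of navigation distance, success and time are not linked to the primary result, and they are themselves observed after the arm is visible.

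**Working it through.** **1. The plan's sample size.** Inputs from Section 4 (Sample size calculation): yields of 70% and 90%, 80% power, two-sided 0.05, 1:1 allocation. With unpooled variance:

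n = (1.960 + 0.842)² × (0.7×0.3 + 0.9×0.1) / 0.2² = 7.849 × 0.30 / 0.04 = 58.87 (using unrounded normal quantiles), rounded up to 59.

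This agrees with the plan: "A group size of 59 patients per arm has been derived". The sample size is not in dispute here.

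**2. Is the arm visible before localisation?**

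| Place | Arm-specific step | Position relative to localisation |
|---|---|---|
| Section 3 | Fluorescein | Before the robotic procedure |
| Section 5, numbered list | Fluorescein, step 2 | Before step 5 |
| Section 5, Steps during the procedure | Fluorescein | Described before target identification |
| Section 5, Preparation before the procedure | Locking device and probe | Before the procedure |

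Every described sequence reveals the arm first. That the operator notices is an inference, but a strong one.

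**3. Where does the shared phase end?** Section 3 and the numbered list have the needle enter the tissue before the probe is fitted. Steps during the procedure says instead "Once the nodule is localized, an 18G needle with the Confocal Miniprobe™ inside will be introduced". On the first account the shared phase could run through the puncture; on the second it ends at localisation. The passages conflict, and the answer decides how late disclosure can be.

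**4. Sensitivity to an assumed shift.** Let a and b be first-pass successes in the control and nCLE arms, with a ~ Bin(59, 0.70) and b ~ Bin(59, 0.70 + δ). There is no true nCLE effect; δ is the bias. The statistic is

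z = (b/59 − a/59) / √[2p̄(1 − p̄)/59], with p̄ = (a + b)/118.

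The chance of a false finding for nCLE is the sum of the joint probabilities over all (a, b) with z > 1.96, by exact enumeration.

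| Assumed shift δ | P(significant, favouring nCLE) |
|---|---|
| 0 | 2.6% |
| +1 point | 3.4% |
| +2 points | 4.4% |
| +3 points | 5.7% |
| +5 points | 9.0% |
| +10 points | 24.5% |

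Applying the plan's switch to Fisher's exact test when a count is below 5 leaves these values unchanged to the first decimal.

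**5. The opposite direction.** If extra effort goes to the control arm and lifts it from 70% to 75%, against 90% with nCLE, power under the same chi-squared test falls from 80.5% to 59.6%.

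**6. The exclusion route, for illustration.** If 41 of 59 succeed (69.5%) and three would-be failures in that arm are instead excluded as not localisable, the yield becomes 41/56 = 73.2%, a rise of 3.7 points. The count of three is an assumption; the documents give no localisation-failure rate.

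**The case against.** An operator who cannot be masked is normal in device trials. Guidance is the same in both arms, the pathologists do not know the nCLE results, and lesion characteristics and navigation measures are compared by arm, so a gross imbalance might show. Nothing in the documents supports a particular shift, and 10 points is half of the hypothesised effect. At +1 or +2 points the consequence is slight; at +3 the total two-sided error is 6.7% against 5.2% with no shift. All of this stands as a limit on the size of the claim. None of it closes the opening, because these safeguards do not correct the primary comparison.

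Delayed disclosure also meets practical limits. The dye must either be given without the operator knowing, with monitoring for allergic reactions preserved, or be fitted to whatever timing the sponsor settles. Probe assembly has several steps, and the Summary puts the added endoscopy time at no more than 10 minutes. The navigation measures in Section 7 refer to the guide or the Miniprobe, so they cannot simply be relabelled as baseline checks. These objections also stand, and they shape the fix.

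Two stronger readings are tempting. A reader might infer that everything before imaging could be masked. With a pre-loaded probe the puncture cannot be. A reader might also take Steps during the procedure as saying that the arms are identical until localisation. That text describes only the nCLE procedure and compares nothing; the support comes from the numbered list.

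**Conclusion.** The concern holds as an avoidable opening for performance and exclusion bias in the primary comparison. It rests on the inference that the operator knows the arm, which the available text does not state. Figure 3, the two-arm flow, could not be read in the available copy, and some pages were missing from it.

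Direction and size are unknown. The range from 3.4% (1 point) to 24.5% (10 points), against 2.6% with no bias, shows what assumed shifts would do; it does not estimate what will happen. A reader might conclude that the trial's result will be biased or is invalid. The documents show opportunity, not occurrence, and do not support that. The change should be made because it is cheap, leaves 59 per arm and the endpoint as they are, and also makes the localisation exclusion blind to arm. Confidence is moderate.

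**What to change.** 1. In Section 3, state that allocation is concealed from the operator and disclosed, or the patient randomised, only after localisation success or failure has been recorded with a time stamp. Another team member holds the allocation.
2. State that arm-specific preparation is done out of the operator's view or after disclosure.
3. In Section 7, define navigation time, distance and success up to that time stamp in the same way in both arms, without reference to the Miniprobe, and report them as balance checks.
4. Reconcile the fluorescein-timing statements in Section 3, Steps during the procedure and the numbered list. Reconcile also whether the needle enters the lesion before the probe is fitted or with it pre-loaded. Both decide how late disclosure can be. No dye dose or timing is proposed here.

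Costs: protocol wording, an in-room disclosure step, a few minutes of preparation after localisation, and redefined navigation measures. If randomisation itself is moved, more patients may need to consent to cover localisation failures; the documents do not give that rate. Any part of alignment or puncture after disclosure stays unmasked, and the report should say so.
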